8.3.7 European Quality of Life - 5 Dimensions-3 Level Questionnaire

The EQ-5D-3L questionnaire is a standardized instrument developed as a measure of health-related QoL that can be used in a wide range of health conditions and treatments. The EQ-5D-3L consists of a descriptive system and the EQ-5D-3L VAS.

The descriptive system comprises 5 questions on the following dimensions: mobility, self care, usual activities, pain/discomfort and psychological status (anxiety/depression) with 3 possible answers for each item (1=no problem, 2=moderate problem, 3=severe problem). The scores on these 5 dimensions (domain scores) represent a health profile for the subject and can be converted to a single summary index with a maximum score of 1 using a pre-defined algorithm and table of scores. The maximum index score of 1 indicates the best health state, by contrast with the scores of individual questions from the descriptive system, where higher scores indicate more severe or frequent problems.

The EQ-5D-3L VAS records the subject's self-rated health on a vertical 0 to 100 scale, with 100 indicating the best health status.

[Section 14.4](#) shows the full questionnaire together with the derivation of the EQ-5D-3L index score (Dolan 1997).

The 5 domain scores, derived EQ-5D-3L index score and VAS scores will be listed by treatment group for each subject at each visit, including changes from Baseline for the EQ-5D-3L index score and VAS score.

The number and percentage of subjects giving each categorical response (1, 2 or 3) to the questions on the EQ-5D-3L domains will be summarized by visit and treatment group, overall and by Baseline Hurley Stage. Shifts from Baseline in the domain scores at each post-Baseline visit will also be presented by treatment group, overall and by Baseline Hurley Stage. Any questions with a missing or ambiguous response (eg, 2 boxes ticked for a single dimension) will be counted in the category "Missing" in the categorical summaries of the EQ-5D-3L domain scores.

The numeric domain scores and changes from Baseline will also be summarized by treatment group, overall and by Baseline Hurley Stage as continuous variables using summary statistics at each visit. Any questions with an ambiguous response (eg, 2 boxes ticked for a single dimension) will be regarded as missing for the tabulations.

The derived EQ-5D-3L index score and VAS scores will be summarized using descriptive statistics together with changes from Baseline, by visit, treatment group, overall and by Baseline Hurley Stage.

8.3.8 Hurley Stage

The Hurley Stage is a severity classification for HS that was developed in 1989 and is widely used for the determination of the severity of HS (Hurley, 1989). Stage I HS is the most common

(68% of patients), while Stage II occurs in about 28% of patients and Stage III only occurs in about 4% of patients.

The Hurley Stage is defined by the following criteria and will be assessed for each anatomical region as part of the lesion count assessment ([Section 8.1](#)):

- Stage I: Abscess formation, single or multiple, without sinus tracts and cicatrization (scarring)
- Stage II: Recurrent abscesses with tract formation and cicatrization, single or multiple, widely separated lesions
- Stage III: Diffuse or near diffuse involvement, or multiple interconnected tracts and abscesses across the entire area

The Hurley Stage for each anatomical region will be recorded directly on the eCRF and the overall worst Hurley Stage (ie, the highest Hurley Stage) will be derived automatically in the database across all reported anatomical regions. Hurley Stage will be listed by treatment group, anatomical region and subject at each visit.

A categorical summary of the overall worst Hurley Stage at each visit will be presented by treatment group. The changes from Baseline in the overall worst Hurley Stage will be summarized in shift tables by treatment group and post-Baseline visit. The denominator for the percentages will be the number of subjects in the FAS with non-missing overall worst Hurley Stage in the respective treatment group and visit.

8.3.9 Erythema assessment

The erythema assessment will be recorded as specified in [Section 8.1](#).

Erythema assessment results will be listed by treatment group, subject, visit and anatomical region. In addition, the overall worst erythema (highest score) will be derived automatically in the database across all reported anatomical regions and will be listed by treatment group, subject and visit.

A categorical summary of the overall worst erythema scores, showing the number and percentage of subjects within each category at each visit, will be presented by treatment group, overall and by Baseline Hurley Stage. The denominator for the percentages will be based on the number of subjects in the FAS in the given treatment group, Baseline Hurley Stage and visit with non-missing data for worst erythema.

The changes from Baseline in the degree of erythema will be summarized in shift tables by treatment group, post-Baseline visit, overall and by Baseline Hurley Stage. The denominator for the percentages will be based on the number of subjects in the FAS in the given treatment group, Baseline Hurley Stage and visit with non-missing data for the Baseline worst erythema score at Baseline and at the respective visits.

8.3.10 Hospital Anxiety and Depression Scale

The HADS was chosen for its well established psychometric properties and its use in clinical research on biological therapy in subjects with other inflammatory skin diseases (Dauden et al, 2009; Langley et al, 2010).

The HADS is a commonly used instrument to determine the levels of anxiety and depression that a subject is experiencing. The HADS is a 14-item scale that generates ordinal data. Seven items relate to anxiety (assessed in the HADS-A) and seven relate to depression (assessed in the HADS-D). Individual item scores range from 0 to 3 and are summed to give a total score on each of the individual HADS-A and HADS-D scales. These total scores range from 0 to 21 with higher scores indicating a worse state.

The full HADS questionnaire is shown in [Section 14.5](#) together with the derivation of the total HADS-A and HADS-D scores.

Scores for each item on the HADS-A and HADS-D will be listed at each visit by treatment group and subject. This listing will also include the total HADS-A and HADS-D scores together with the changes from Baseline in the total HADS-A and total HADS-D scores at each visit. Summary statistics will be presented by treatment group and Baseline Hurley Stage for the observed total HADS-A and HADS-D scores together with changes from Baseline at each visit.

8.4 High Sensitivity C-Reactive Protein

Concentrations of hsCRP will be listed by treatment group, subject and visit for each subject including changes from Baseline and ratio to Baseline. The latter will be calculated as follows:

$$\text{Ratio to Baseline} = \text{hsCRP at post-Baseline} / \text{hsCRP at Baseline visit}$$

Observed values, changes from Baseline and ratio to Baseline will be summarized by treatment group, Baseline Hurley Stage and visit. For the observed values and changes from Baseline, summary statistics will include n, arithmetic mean, SD, median, Q1, Q3, minimum and maximum. For the ratio to Baseline, summary statistics will include n, geometric mean, geoCV, median, Q1, Q3, minimum and maximum.

The rules for handling any values that are BLO are described in [Section 4.2.1](#).

9 PHARMACOKINETICS AND PHARMACODYNAMICS

9.1 Pharmacokinetics

There will be no calculation of PK parameters for this study. The analysis of PK data for this study will focus on the trough plasma concentrations of BKZ only. Any additional PK analyses will be performed only if required.

The actual blood sampling times for BKZ concentrations will be obtained in days relative to the start time of the first dose of IMP for all sampling time points.

Individual blood sampling times and concentrations of BKZ will be listed for the SS and will include the actual sampling time in days relative to the first dose of IMP. Individual concentrations will be summarized at each scheduled time point based on the PK-PPS, using n, mean, median, SD, minimum, maximum, geometric mean and 95% CI, and geoCV (assuming log normally distributed data).

Individual concentration versus time (day) profiles will be presented graphically on linear and semi-logarithmic scales with all subjects overlaid on the same plot (spaghetti plots). Geometric mean profiles of BKZ will also be presented on both linear and semi-logarithmic scale respectively with and without the corresponding lower and upper limit of the 95% CI. All semi-logarithmic plots will include the LLOQ marked on the y axis.

The following rules will apply for PK data listings and summaries:

- Values below the LLOQ will be reported as BLQ
- Descriptive statistics of concentrations will be calculated if at most $\frac{1}{3}$ of the individual data points are missing or are not quantifiable ($<LLOQ$). Values that are BLQ will be replaced by the numerical values of the $LLOQ/2$ in this instance. However, if $n \leq 3$, then only n , minimum and maximum will be presented (where 'n' refers to the number of quantifiable values). The other descriptive statistics will be left blank.
- The 95% CI for the geometric mean should be left blank if the SD (or equivalently, the geoCV) is 0
- The geoCV (%) will be calculated using the following formula where SD is the standard deviation from the log transformed data

$$geoCV = 100 \times \sqrt{e^{SD^2} - 1}$$

9.2 Pharmacodynamics

Blood sampling for exploratory PD analyses will be taken for the evaluation of the following:

- Flow cytometry by fluorescence activated cell sorting analysis which might include, but will not be limited to: cluster of differentiation (CD) CD3, CD19, CD4, CD8, and CD69.
- Candidate biomarkers might include, but will not be limited to: IL-17A/IL-17F pathway signaling and HS (eg, IL-17A, IL-17F, IL-23, IL-6, TNF, DC-STAMP, and circulating osteoclast precursors).

The results for all exploratory PD variables will be listed by treatment group, subject and visit, together with the changes from Baseline, based on the SS. Observed values and changes from Baseline will be summarized by treatment group based on the PD-PPS.

Figures of mean and mean changes from Baseline (including 95% CIs for the mean and mean change from Baseline) will be presented with separate plots for each variable and all 3 treatment groups overlaid on the same plot.

The rules for handling any values that are BLQ or ALQ are described in [Section 4.2.3](#).

10 IMMUNOLOGICAL ANALYSES

All immunological analyses will be performed for the PK-PPS. In this study, this will comprise an analysis of anti-BKZ antibody data only which will be listed and summarized at each scheduled visit, and the rate of anti-BKZ antibody positive subjects will be calculated.

The results of the anti-BKZ antibody analysis will be listed by treatment group and visit based on the SS. This will include the screening assay, confirmatory assay, titre (if applicable) and confirmation of whether or not the sample contains BKZ concentration levels above the drug tolerance.

A cut point will be determined by the bioanalytical laboratory that will be used to determine the status of anti-BKZ antibody as above the cut point (ACP) or below the cut point (BCP). For any anti-BKZ antibody levels that are ACP, a further confirmatory assay will be performed, the results of which will be determined as either 'confirmed positive' (CP) or 'not confirmed

positive' (NCP). For samples that are CP, a further titre assay will be performed and the anti-BKZ antibody titre will be reported.

The following definitions will be applied:

- An anti-BKZ antibody status of positive will be concluded for any subject with an anti-BKZ antibody level that is ACP and CP at any time point
- An anti-BKZ antibody status of negative will be concluded for any subject with an anti-BKZ antibody level that is either BCP or ACP and NCP at any time point
- A subject will be classified as having anti-BKZ antibody positivity at Baseline if the Day 1, predose result is ACP and CP
- A subject will be classified as having treatment-induced anti-BKZ antibody positivity when meeting 1 of the following criteria:
 - The Baseline result is either BCP or ACP and NCP, and at least 1 post-Baseline time point is ACP and CP
 - The Baseline result is positive (ACP and CP) and at least 1 post-Baseline measurement shows a pre-defined fold increase in titre from the Baseline value (the fold increase from Baseline required to meet these criteria will be defined with the development of the assay and will be included in the TFLs)
- A subject will be classified as overall positive if at least 1 post-Baseline measurement is ACP and CP (this includes subject who have negative results at Baseline)
- A subject will be classified as overall negative if at all post-Baseline visits the anti-BKZ antibody status is negative (this includes subjects who have positive [ACP and CP] results at Baseline)

The number and percentage of subjects with a positive and negative anti-BKZ antibody status will be summarized at each visit and overall. This summary will exclude any samples with BKZ concentrations confirmed to be above the drug tolerance.

In addition, the first occurrence of treatment-induced anti-BKZ antibody positivity (based on the definitions above) will be summarized at each post-Baseline visit. This tabulation will present the number and percentage of subjects at each post-Baseline visit who fulfill at least 1 of the above defined criteria for treatment-induced positivity; subjects will be counted in the numerator based on the earliest visit at which 1 of these criteria is fulfilled. At other visits, subjects will be counted in the denominator (assuming a measurement is available). This summary will exclude any samples with BKZ concentrations confirmed to be above the drug tolerance.

For all tabulations, percentages will be calculated based on the number of subjects with non-missing data and anti-BKZ antibody levels that are not flagged as containing BKZ concentration levels above the drug tolerance at each respective visit.

A separate listing will be presented showing the BKZ concentrations and anti-BKZ antibody measurements in the same output in adjacent columns, based on the PK-PPS. The listing will include the BKZ concentration, anti-BKZ antibody status (ACP or BCP) and confirmatory assay results if applicable (NCP or CP), together with the titre for results that are CP. In addition, the time since the previous administration of IMP will be reported (in days).

Finally, individual subject plots will be presented displaying the anti-BKZ antibody titre and BKZ concentrations overlaid on the same figure. The figure will also show the timing and dose of each administration of BKZ received during the study. The anti-BKZ antibody data will be plotted using a semi-logarithmic scale. This figure will exclude any samples with BKZ concentrations confirmed to be above the drug tolerance.

The rules for handling values that are BLQ in the BKZ concentration data are described in [Section 4.2.2](#). For the anti-BKZ antibody data, any negative results for which there are no titres available at a specific visit will be substituted with 0.001 for the purpose of the figure.

11 SAFETY ANALYSES

All analysis of safety variables will be performed using the SS.

11.1 Extent of exposure

All IMP administration details (including date, time and location of injection) will be listed.

The percentage of injections administered will be included in the listing based on the number of planned injections. For subjects completing the study this will be 17 injections. The number of planned injections for subjects who withdraw early from the study will be reduced according to the number of injections planned up to EW visit.

All IMP administration details (including date, time and location of injection) will be listed. The percentage of injections administered will be included in the listing based on the number of planned injections. For subjects completing the study this will be 17 injections. The number of planned injections for subjects who withdraw early from the study will be reduced according to the number of injections planned up to EW visit.

The duration of exposure to BKZ and PBO (days) will be calculated as follows:

$$\text{Exposure} = (\text{Date of Last Dose} - \text{Date of First Dose}) + 140 \text{ days}$$

The duration of exposure to ADA (days) will be calculated as follows:

$$\text{Exposure} = (\text{Date of Last Dose} - \text{Date of First Dose}) + 100 \text{ days}$$

The number of days added to the BKZ and ADA exposure calculations are 5 times the half-life of each drug, respectively: 5 x 28 days for BKZ and 5 x 20 days for ADA. The number of days added to PBO is set to 140 days in order for PBO exposure to be comparable to that of BKZ.

Missed doses will not be accounted for in the calculation above.

Duration of exposure will be listed for each subject and summarized using descriptive statistics.

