5.1.2 Study duration per subject

For each subject, the study will last a maximum of 34 weeks. This includes the following study period durations:

- Screening Period: ≥ 2 weeks up to a maximum of 4 weeks, from the time of informed consent up to randomization and administration of IMP at Baseline (Visit 2).
- Treatment Period: Up to 12 weeks, from the administration of IMP at Baseline (Visit 2) to the assessment of the primary efficacy variable at Week 12 (Visit 11).
- SFU Period: Up to 20 weeks, from the last dose of IMP at Week 10 (Visit 10) to the SFU Visit at Week 30 (Visit 12).

The end of the study is defined as the date of the last visit of the last subject in the study.

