11.2 Adverse events

Adverse events with a start date prior to the first dose of IMP will be defined as pre-treatment AEs. A treatment-emergent AE (TEAE) is defined as any AE with a start date/time at the time of or after the first dose of IMP up until 140 days after the last dose of IMP. Any AE with onset later than 140 days after the last dose of IMP will not be considered as treatment-emergent and therefore will not be included in the tabulations of TEAEs. Where dates are missing or partially missing, AEs will be assumed to be treatment-emergent, unless there is clear evidence to suggest that the AE started prior to the first dose of IMP or later than the defined cutoff for TEAEs.

Handling of missing dates/times for classification of AEs as TEAEs is described in [Section 4.2.4](#).

All AEs will be recorded in the eCRF from informed consent until study completion or termination. All AEs will be coded and categorized by intensity (mild/moderate/severe) and relationship to IMP (related/not related).

An overview of the number and percentage of subjects who experience TEAEs will be presented by treatment group, based on the SS. This tabulation will include the number and percentage of subjects with any TEAEs, serious TEAEs, related TEAEs, discontinuation due to TEAEs, severe TEAEs, AEs leading to death and TEAEs leading to death; event counts will also be included.

In addition, the following summaries will be presented by treatment group, SOC, high level term (HLT) and PT, based on the SS:

- Incidence of TEAEs
- Incidence of TEAEs, stratified by overall anti-BKZ antibody status (positive/negative) as defined in [Section 10](#)
- Incidence of serious TEAEs
- Incidence of non-serious TEAEs
- Incidence of TEAEs by relationship
- Incidence of TEAEs by maximum relationship
- Incidence of TEAEs by maximum intensity
- Incidence of fatal TEAEs by relationship
- Incidence of non-serious TEAEs by relationship
- Incidence of serious TEAEs by relationship
- Incidence of non-serious TEAEs above threshold of 5% of subjects
- Incidence of non-serious TEAEs above threshold of 5% of subjects by relationship
- Incidence of TEAEs by SOC and PT (including the number and percentage of subjects and individual subject numbers for each PT stratified by intensity, relationship and seriousness)

In addition, separate summaries by treatment group, SOC, HLT and PT will be included for the following AEs for special monitoring (AESM):

- Major cardiovascular events

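### SAP 11.1 gives adalimumab 40 days less exposure than the other arms over the same dosing span and TEAE window, with no cut-off at death or study exit, so the exposure summary is not comparable across arms

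*SAP*

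**What the plan says.** SAP 11.1 (Extent of exposure) has two formulas. Both take the date of the last dose minus the date of the first dose. The first adds 140 days and applies to bimekizumab and placebo; the second adds 100 days and applies to adalimumab. The additions are five half-lives: "5 x 28 days for BKZ and 5 x 20 days for ADA". Placebo has no half-life, and its figure is set by a different argument: "The number of days added to PBO is set to 140 days in order for PBO exposure to be comparable to that of BKZ".

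On adjustments, the section says only this: "Missed doses will not be accounted for in the calculation above". It states no limit at death, last contact or study termination. On use, it says: "Duration of exposure will be listed for each subject and summarized using descriptive statistics". Protocol 15.8 requires extent of exposure to be presented by treatment group.

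SAP 11.2 (Adverse events) defines a TEAE by onset "at the time of or after the first dose of IMP up until 140 days after the last dose of IMP", with no distinction by arm. On collection it says: "All AEs will be recorded in the eCRF from informed consent until study completion or termination". The AE tables give numbers and percentages of subjects, and event counts.

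**The concern.** The three arms run on one calendar. In Protocol Table 7-1 the first injections are at Baseline and the last at Week 10 in every arm, and Protocol 5.1.1 and 5.1.2 place the Safety Follow-Up (SFU) Visit 20 weeks after the last dose, at Week 30 for a completer. Any difference in full-course exposure between arms therefore comes from the formula and not from how subjects were treated or followed.

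The SAP is also not uniform in its principle. For placebo it sets half-life aside so that the arm can be compared with bimekizumab, but it does not do so for adalimumab.

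The missing cut-off is a second problem. Protocol 6.3 only encourages subjects who withdraw consent to attend the SFU Visit, and it foresees loss to follow-up. Such subjects still receive the full 140 or 100 days.

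The exposure summary is the only planned by-arm summary of time that could be set beside the event counts. SAP 5.1 does define days on IMP, but assigns it only to the discontinuation listing.

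**Working it through.** **Inputs**
- Days added: 5 × 28 = 140 (bimekizumab), 5 × 20 = 100 (adalimumab), 140 (placebo, by rule). SAP 11.1. The plan's own figures are reproduced.
- Last minus first dose, full course: Week 10 = 10 × 7 = 70 days, all arms. Protocol Table 7-1.
- TEAE window: to 140 days after the last dose, all arms. SAP 11.2.
- SFU Visit for a completer: Week 30 = 30 × 7 = 210 days. Protocol 5.1.2.

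**Full course, followed to the SFU Visit**

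| Arm | Exposure (SAP 11.1) | TEAE window (SAP 11.2) | Difference |
|---|---|---|---|
| Bimekizumab | 70 + 140 = 210 | 70 + 140 = 210 | 0 |
| Placebo | 70 + 140 = 210 | 70 + 140 = 210 | 0 |
| Adalimumab | 70 + 100 = 170 | 70 + 140 = 210 | −40 |

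The share of the adalimumab TEAE window outside stated exposure is 40/210 = 19.0%. If someone divided adalimumab events by this exposure, the rate would be overstated by 210/170 − 1 = 23.5%. These are nominal days; the SFU Visit has a window of −3 to +7 days.

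**Early exit**

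Let a subject leave x days after the last dose (x < 140) without attending the SFU Visit. AE time observed after the last dose is x, so credited minus observed time is:
- bimekizumab or placebo: 140 − x
- adalimumab: 100 − x, which becomes negative once x exceeds 100

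At x = 14 the excess is 126 days and 86 days respectively. With a last dose at Week 4 (28 days), exposure is 28 + 140 = 168 or 28 + 100 = 128, against 28 + 14 = 42 days observed.

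**Arm means**

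The documents give no dropout figure. As an assumption, let a share d leave 14 days after a Week 4 last dose while the rest complete:
- mean exposure, bimekizumab or placebo = (1 − d) × 210 + d × 168
- mean exposure, adalimumab = (1 − d) × 170 + d × 128
- mean observed = (1 − d) × 210 + d × 42

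| d | Observed | Bimekizumab/placebo exposure (ratio to observed) | Adalimumab exposure (ratio to observed) |
|---|---|---|---|
| 0% | 210.0 | 210.0 (1.00) | 170.0 (0.81) |
| 10% | 193.2 | 205.8 (1.07) | 165.8 (0.86) |
| 20% | 176.4 | 201.6 (1.14) | 161.6 (0.92) |
| 30% | 159.6 | 197.4 (1.24) | 157.4 (0.99) |

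The ratio of exposure to observed time differs between arms and moves with dropout, so no single correction factor would repair the table afterwards.

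**The case against.** The strongest reply is that exposure and the TEAE window are different quantities and need not match. SAP 11.1 measures how long drug persists, the 140/100 split is deliberate and explained by half-life, and persistence does not stop when a subject leaves the study. A common 140-day AE window also treats the arms alike.

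Much of this stands. The split is not an arithmetic error, and on a persistence reading only death clearly calls for truncation. That reading does not cover placebo, however, whose 140 days rest on comparability alone.

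A reader might infer more than the documents support, in three ways:
- **That the planned adalimumab AE results are inflated in bimekizumab's favour.** They are not. SAP 11.2 plans subject counts, percentages and event counts, with no rate per unit of exposure. No planned TEAE figure changes if 100 becomes 140.
- **That exposure and event counts cover different time in every arm.** Bimekizumab and placebo subjects followed to the SFU Visit have matching windows, and so do early withdrawers in those arms who attend it.
- **That nothing is collected after exit.** Protocol 11.1.2.3 collects SAEs for 30 further days, and SAEs thought to be related to IMP without time limit.

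It is also true that adalimumab events 101 to 140 days after the last dose can be found in the listings, which show days since the most recent dose. That helps someone reading listings but does not make the summary comparable.

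**Conclusion.** The point holds as a fault in a descriptive safety table that the protocol requires. For a full course the table would show 210, 210 and 170 days for bimekizumab, placebo and adalimumab, when all three arms have 210 days of TEAE counting. The 40-day gap follows directly from the text and needs no assumption beyond the planned schedule.

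The 23.5% is conditional. It describes a full-course adalimumab arm followed to 140 days, and arises only if someone forms a rate the SAP does not plan. The size of the early-exit effect depends on dropout timing and share, which are assumed above. Its existence follows from the missing cut-off.

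The correction is worth making because it is cheap, but no planned efficacy or TEAE result depends on it.

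**What to change.** In SAP 11.1, add one time-at-risk measure for all arms, running from the first dose to the earliest of last dose plus 140 days, last contact, or death. Use one day-count convention throughout: a completer has 210 days by simple difference, or 211 if both end days are counted. Say how an SAE reported in the 30 days after study exit is treated.

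Summarise this measure by arm beside dosing duration (last dose minus first dose plus 1, already defined in SAP 5.1). Keep the five-half-life figures, truncated at death, as separately labelled rows, with a note that they are not person-time for TEAEs.

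The cost is one derivation and some SAP wording. Dose dates are already listed and the date of final contact is in the SAP 5.1 disposition listing, so no new collection is needed. The main visible change is that adalimumab completers rise from about 170 to 210 days. Bimekizumab and placebo means fall where subjects leave early: in the 10% example above, from 205.8 to 193.2 days. In the same example adalimumab moves from 165.8 to 193.2, so all arms agree.
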